MACE, the composite endpoint that includes Death (all cause), Myocardial Infarction (MI) and Revascularization for myocardial ischemia, will be the primary outcome measure after randomization and the index CABG. Each randomized subject (either in Endoscopic or in Open harvesting group) will be followed after the index CABG to capture the time-to-MACE event where an ‘EVENT’ will be defined as either death (all cause) or an MI or a revascularization procedure during the follow-up period. Total follow-up period will be 6.5 years of which the first 4.5 years will be active follow-up (using in-clinic visit or by telephone) period and will be carried out by the site personnel. The remaining 2 years will be passive follow-up which will be carried out centrally by the chair’s office staff using the VA patient database. A minimum of 1 year of active follow-up will be used for subjects who will be randomized at the tail end of the 3-year projected enrollment period of the study. The subjects

who will either be lost to follow-up or will not experience an 'EVENT' before the end of the follow-up period will be considered as right censored.

The primary analysis of such time-to-Mace event data will include the events only from the active follow-up period (which is 4.5 years). The secondary analysis will include events from the entire 6.5 years of follow-up period.

Survival analysis techniques will be used to analyze the time-to-MACE event data for both primary and secondary analyses.

Kaplan-Meier analysis, a nonparametric method, will be used to estimate the survival (not experiencing MACE) over time in the two harvesting groups and a log-rank statistic will be used to test the equality of the survival function estimates in the two groups (the null hypothesis).

Cox's Proportional Hazards models will be used to investigate the effect of harvesting technique on the time until MACE adjusted for other potential influential variables, such as, age, gender, harvester's experience etc.

3. Secondary Outcomes Measures

One and Three-year MACE: This composite endpoint consists of

- i. Death (all cause);
- ii. Myocardial Infarction and
- iii. Revascularization for myocardial ischemia.

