5.4 General Considerations

This section details general policies to be used for the statistical analyses. Departures from these general policies may be given in the specific detailed sections of this statistical analysis plan. When this situation occurs, the rules set forth in the specific section take precedence over the general policies. The following policies will be applied to all data presentations and analyses.

- All p-values will be rounded to 3 decimal places. All p-values that round to 0.000 will be presented as ‘<0.001’ and p-values that round to 1.000 will be presented as ‘>0.999’. Any p-value $\leq \alpha$ will be considered statistically significant and will be marked with one asterisk (e.g., 0.026*).
- Summary statistics will consist of the number and percentage of responses in each category for discrete variables, and the mean, median, standard deviation (SD), minimum, and maximum for continuous variables.
- All mean and median values will be formatted to one more decimal place than the measured value. Standard deviation values will be formatted to two more decimal places than the measured value.

- All percentages will be rounded to one decimal place. The number and percentage of responses will be presented in the form XX (XX.X), where the percentage is in the parentheses. The decimal of the percentage may be dropped due to space constraints when creating a table.
- All listings will be sorted for presentation in order of treatment group, site number, participant number, and date of procedure or event.
- When necessary for analysis purposes, partial dates will be completed (i.e., turned into complete dates) using the most conservative approach.
- All analysis and summary tables will have the population sample size for each group or treatment group in the column heading.
- Version 9.3 of SAS® or higher will be the statistical software package used to produce all summaries, listings, statistical analyses, and graphs.
- Updated version of MedDRA will be used for adverse event and pre-treatment coding.
- The current version of the World Health Organization (WHO) drug dictionary will be used for the coding of medications.

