equality (null hypothesis) of the survival function estimates across strata (OVH and EVH) will employ either the log-rank or Wilcoxon test. Multivariable survival analyses applying a Cox proportional hazards regression model will be performed to investigate the effect of SVG harvesting technique on time-to-MACE, adjusting for other potentially influential baseline characteristics, such as age, gender, harvester's experience, etc. (TABLE 25). Assumptions of the model (i.e., non-informative censoring, proportional hazards) will be checked. If assumptions appear to be violated, alternative methods will be explored (e.g., piecewise, time-varying covariates). A type I error rate of $\alpha = 0.05$ will be used throughout. Confidence intervals will be two-sided with a 95% confidence level.

The hypothesis for the primary aim of this study is:

H1: A significantly smaller proportion of CABG subjects with SVGs harvested by open technique will experience MACE post-surgery compared to CABG subjects with SVGs harvested by endoscopic technique during the active follow-up period.

The hypothesis for the primary aim of this study will be supported when an increased risk of MACE is observed among participants randomized to EVH, confirmed with a hazards ratio (HR) > 1.00 for EVH vs. OVH and a significant corresponding p -value $< \alpha$.

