7.2 Secondary Outcomes

Secondary objectives of this study include investigating the impact of SVG harvesting techniques – OVH vs. EVH on MACE at one and three-years postoperatively and over the entire follow-up period (active and passive, ~ 6.5 years) of the study postoperatively. The proportion of participants experiencing a MACE (yes/no) in the first year of follow-up after index CABG surgery date will be calculated, both collectively and by SVG harvesting technique, OVH vs. EVH. These two proportions will be compared using Pearson's chi-square test. The proportion of participants experiencing a MACE (yes-1/no-0) in the three years of follow-up after index CABG surgery date will be similarly analyzed (TABLE 26).

Assessing MACE over the entire follow-up period (active and passive) of the study postoperatively will be analyzed similarly (TABLE 21, FIGURE 2, TABLE 25) to the primary outcome with now the outcome being time (from index CABG surgery date) until the event of interest, MACE, or time-to-MACE during the entire follow-up (~ 6.5 years). Events from both the active and passive follow-up periods will be considered, whereas the primary analysis only included events from the active follow-up period. Only the first event among participants will be considered as the MACE event.

The hypotheses for the secondary aims of this study are:

H2: One-year composite MACE rate will be 6 percentage points lower in the open harvesting group and three-year composite MACE rates will be at least 8-10 percentage points lower in the open vein harvesting group compared to the endoscopic vein harvesting group.

H3: A significant smaller proportion of CABG subjects with SVGs harvested by open technique will experience MACE post-surgery compared to CABG subjects with SVGs harvested by endoscopic technique during the entire follow-up period.

The hypothesis H2 will be supported when the percent of participants experiencing MACE at one-year is 6% and at least 8% greater at three-years among those randomized to EVH vs. OVH, with a significant corresponding *p*-value < α observed for each test. The hypothesis H3 will be supported when an increased risk of MACE is observed among participants randomized to EVH, confirmed with a hazards ratio (HR) > 1.00 for EVH vs. OVH and a significant corresponding *p*-value. A total (recurrent) event analysis at various time points will also be explored comparing EVH and OVH.

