Center	Rate of Reporting	Participant ID	Protocol Non-Compliance Code	Date of Deviation
Albuquerque (501)				
...				
... and so on				

FIGURE 2: Kaplan-Meier Survival Curves

[figure not shown]

TABLE 25: MACE, Active Follow-up: Results of Multivariable Cox Proportional Hazards Regression Model

Parameter	DF	Parameter Estimate	Standard Error	Chi-Square Test Statistic	p-value	Hazard Ratio	95% Hazard CI
EVH (vs. OVH)							
Covariate 1							
...							
... and so on							

TABLE 26: Major Adverse Cardiac Events at 1-year and 3-year, by Treatment

		OVH		EVH		Total		p-value
		N	%	N	%	N	%	
1-Year	MACE							
	Death							----
	MI							----
	RR							----
3-Year	MACE							
	Death							----
	MI							----
	RR							----

TABLE 27: Leg Incision Healing by Treatment

	OVH		EVH		Total		p-value
	N	%	N	%	N	%	
No Disturbance							----
Complication (Any Disturbance)							

TABLE 28: Leg Incision Healing by Treatment: Results of Multivariable Logistic Regression Model

Parameter	DF	Parameter Estimate	Standard Error	Chi-Square Test Statistic	p-value	Odds Ratio	95% CI
EVH (vs. OVH)							
Covariate 1							
...							
... and so on							

TABLE 29: Seattle Angina Questionnaire: Change from Baseline by Treatment

			OVH		EVH		Total		p-value
			N	%	N	%	N	%	
[Component scale]	6-week	Improved							
		No Change							----
		Worsened							-----
	12-month	Improved							
		No Change							----
		Worsened							-----

* No change = (mean score change < 5)

TABLE 30: Seattle Angina Questionnaire: Results of ANCOVA Model

		Parameter	DF	Parameter Estimate	Standard Error	t-Test Statistic	p-value
[Component scale]	[6-week /12-month]	Intercept					
		Baseline Score					
		EVH (vs. OVH)					
		Interaction (if needed)					

TABLE 31: Impact and Severity of Incisional Leg Pain at by Treatment

		OVH		EVH		Total		p-value
		N	%	N	%	N	%	
Discharge	Little or no impact (impact score ≤ 50)							
	Some impact ($50 < \text{impact score} \leq 57$)							----
	Substantial impact ($57 < \text{impact score} \leq 63$)							----
	Severe impact (impact score > 63)							----
	Severe (per severity rating) (Score of 3 or above)							
6-Weeks	Little or no impact (impact score ≤ 50)							
	Some impact ($50 < \text{impact score} \leq 57$)							----
	Substantial impact ($57 < \text{impact score} \leq 63$)							----
	Severe impact (impact score > 63)							----
	Severe (per severity rating) (Score of 3 or above)							

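### SAP 7.1 judges H1 at 0.05 after interim efficacy looks without tying that level to the DMC's boundary, and it departs from the protocol's log-rank test without naming the one test that decides H1

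*SAP*

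**What the plan says.** **Level.** Protocol XVII.D.1 tests the primary outcome two-sided at 5%. Protocol XVII.F says that repeated testing inflates type I error and presents group-sequential boundaries as the way to hold the overall rate at 5%. SAP 5.5 plans about eight interim analyses of the primary outcome. SAP 5.5.1 lets the DMC recommend stopping for a difference large enough to settle the main question. SAP 5.5.1.1 lets it choose a technique, suggesting Haybittle-Peto or Lan-DeMets. SAP 7.1 then gives a type I error rate of 0.05 that "will be used throughout. Confidence intervals will be two-sided with a 95% confidence level". H1 is supported when increased risk with EVH is "confirmed with a hazards ratio (HR) > 1.00 for EVH vs. OVH and a significant corresponding" p-value below alpha. SAP 5.4 adds that any p-value at or below alpha "will be considered statistically significant and will be marked with one asterisk". Neither place mentions the boundary.

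**Test.** Protocol XVII.D.2 says that "a log-rank statistic will be used to test the equality of the survival function estimates in the two groups", and gives Cox models the separate job of adjusted effects. SAP 7.1 says that tests of "equality (null hypothesis) of the survival function estimates across strata (OVH and EVH) will employ either the log-rank or Wilcoxon test". It also plans a Cox model "adjusting for other potentially influential baseline characteristics, such as age, gender" and harvester experience, with the list left open. That model's shell is TABLE 25, "MACE, Active Follow-up: Results of Multivariable Cox Proportional Hazards Regression Model". SAP 7.2 repeats the H1 wording for the full follow-up: "The hypothesis H3 will be supported when an increased risk of MACE is observed among participants randomized to EVH", again with a hazard ratio above 1 and a corresponding p-value of unnamed source.

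**The concern.** Interim looks that can end the trial for efficacy use up part of the 5%. If the final test is still made at 0.05, the total exceeds 5%, and a final p-value between roughly 0.036 and 0.05 could be declared significant when the chosen boundary would say otherwise.

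Separately, log-rank, Wilcoxon and adjusted Cox can fall on different sides of the threshold in the same data. The SAP does not say which of them settles H1 or H3, and the likeliest reading is not the test the protocol named. Protocol XVII.H requires deviations from the protocol to be specified in the SAP; the available SAP text marks none here.

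**Working it through.** **1. The plan's own power figure.** Protocol XVII.B claims 97.5% power with 532 per group for 83.5% versus 91.5% MACE-free. With a pooled variance under the null, z = [0.08 x sqrt(532) - 1.96 x sqrt(2 x 0.125 x 0.875)] / sqrt(0.085 x 0.915 + 0.165 x 0.835) = (1.845 - 0.917) / 0.464 = 2.00, so power is 97.7%. The claim is reproduced closely and assumes a final test at 0.05.

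**2. Look times.** Both documents say the primary outcome cannot usefully be reviewed before year 2, reports are six-monthly, and the DMC meets at 6-9 months and then yearly, at most four times. Recruitment takes 3 years and active follow-up closes at 4-4.5 years. That gives:
- four looks (2, 2.5, 3, 3.5 y; close at 4.0 y) or five (adding 4.0 y; close at 4.5 y) if every report counts;
- two looks (about 2.5 and 3.5 y) if only meetings count.

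**3. Assumptions not in the documents.** Uniform accrual; null hazards of 0.034-0.134 per year, which set the event fractions (for four looks 0.27-0.29, 0.43-0.45, 0.61-0.63, 0.81-0.82); Haybittle-Peto z of 3 or 3.29; and O'Brien-Fleming-type Lan-DeMets spending, either 0.025 per side or 0.05 two-sided. That spending type matches SAP 5.5.1.1, which describes boundaries that are very strict at the first looks.

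**4. Calculation.** Overall error = P(cross at any interim look) + P(no crossing, then |Z| > 1.96 at the end), by recursive integration of the sequential statistic under no true difference. The final level for exactly 5% replaces 1.96 by the value that brings this sum to 0.05.

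| Boundary | 2 looks | 4 looks | 5 looks | Final level for 5% |
|---|---|---|---|---|
| Haybittle-Peto z = 3.29 | 5.03-5.05% | 5.08-5.09% | 5.10-5.11% | 0.049-0.050 |
| Haybittle-Peto z = 3 | 5.11-5.16% | 5.27-5.28% | 5.33-5.35% | 0.046-0.049 |
| Lan-DeMets, 0.025 per side | 5.4-5.7% | 5.7% | 5.8% | 0.040-0.046 |
| Lan-DeMets, 0.05 two-sided | 5.6-5.9% | 5.9% | 6.0% | 0.036-0.044 |

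The two-look range covers closing at 4.0 or 4.5 years. H1 claims only that EVH is worse, so by symmetry its excess over the nominal 2.5% is half: from (5.03 - 5)/2 = 0.015 to (6.04 - 5)/2 = 0.52 percentage points.

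**5. Power after correction.** The claimed 97.5% corresponds to an expected final statistic of 1.96 + 1.96 = 3.92. The strictest final value above is z = 2.09, giving Phi(3.92 - 2.09) = 96.6%. The mildest is z = 1.963, giving Phi(1.957) = 97.5%. Counting early rejections, the range is 97.0-97.5%.

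**6. Which test decides H1.**
- The H1 sentence joins the p-value to a hazard ratio. Log-rank and Wilcoxon tests yield none, and the only SAP shell for the active period that reports one is the adjusted Cox model of TABLE 25.
- That model's covariates are an open list in SAP 7.1. Protocol Appendix D picks predictors by univariate tests but gives no threshold.
- The protocol's null-hypothesis test is the log-rank.
- In null simulations (1,152 patients, 32 harvesters, blocks of 2 and 4, 10,000 trials per setting, assumed covariate effects), each test fixed in advance held its level within Monte Carlo error of about 0.45 points: log-rank 4.3-5.4%, Wilcoxon 4.3-5.1%, adjusted Cox 4.3-5.3%.

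**The case against.** **The boundary is only a guide.** Protocol XVII.F says a crossing means termination should be considered, and the DMC only recommends. If crossings never led to stopping, the final test at 0.05 alone would have 5% error. This stands, and it makes every error figure above an upper bound.

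**Alpha of 0.05 may mean the overall rate.** Protocol XVII.F states that aim, and a boundary carried to its final value meets it. This reading is consistent, but SAP 7.1 does not state it, and an analyst following its H1 sentence would compare p with 0.05. SAP 5.4 is mainly a presentation rule that yields to specific sections, so it neither adds much to the problem nor resolves it.

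**The excess is small.** It is: under Haybittle-Peto at most about 0.35 points two-sided, and 0.03-0.05 points with two looks at z = 3.29.

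**The deciding test is implied.** The hazard-ratio wording does favour the adjusted Cox row. But that leaves a model without fixed covariates deciding H1, in place of the protocol's log-rank.

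**Stronger readings that the documents do not support.** A reader might infer that leaving the test open inflates type I error by itself. No passage describes choosing the most favourable p-value, and each test fixed in advance holds 5%. A reader might also take the eight analyses literally; equally spaced, they give 5.2-6.1%, but eight does not fit six-monthly reports starting at year 2.

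**Conclusion.** The point holds as two gaps in SAP 7.1.

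First, the stated final rule does not secure the protocol's 5% overall error. The excess is at most about 0.35 points two-sided under Haybittle-Peto and about 0.4-1.0 points under O'Brien-Fleming-type Lan-DeMets (0.7-1.0 with four or five looks), and half of that for the direction H1 claims. These sizes rest on the assumed spending form, Haybittle-Peto z and look times, and on treating every crossing as a rejection. It would go too far to say the trial will exceed 5%: it will not if the DMC's boundary is applied through to its final value.

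Second, the SAP adds Wilcoxon to the protocol's log-rank with no rule, and words H1 and H3 so that an adjusted Cox p-value most naturally decides. This is a conflict between documents and an unfixed decision rule, not a demonstrated loss of error control. Both gaps should be closed before the final analysis.

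**What to change.** In SAP 7.1:
- Define 0.05 as the overall two-sided type I error across interim and final analyses. Judge H1 against the final critical value of the boundary the DMC selected (about 0.036-0.050 for the schedules above), and record the boundary and value in the SAP before the final analysis. The choice of boundary stays with the DMC. State that the general rule in SAP 5.4 defers to this for H1.
- Delete the Wilcoxon option. Name the log-rank as the single deciding test for H1, take the direction from the hazard ratio of a named Cox model, and label Wilcoxon and covariate-adjusted Cox results supportive. Name the deciding p-value for H3 in SAP 7.2 in the same way.

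Minor: reconcile the number of looks. SAP 5.5 and Protocol XVII.E say about eight analyses, which does not match the stated schedule, and Protocol XVII.F calls Figure 2 an example for six looks in the text and eight in the caption.

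Cost: a few sentences and one item recorded from the DMC. The final level becomes slightly stricter, and the claimed 97.5% power becomes about 96.6-97.5%.

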7.2 Secondary Outcomes

Secondary objectives of this study include investigating the impact of SVG harvesting techniques – OVH vs. EVH on MACE at one and three-years postoperatively and over the entire follow-up period (active and passive, ~ 6.5 years) of the study postoperatively. The proportion of participants experiencing a MACE (yes/no) in the first year of follow-up after index CABG surgery date will be calculated, both collectively and by SVG harvesting technique, OVH vs. EVH. These two proportions will be compared using Pearson's chi-square test. The proportion of participants experiencing a MACE (yes-1/no-0) in the three years of follow-up after index CABG surgery date will be similarly analyzed (TABLE 26).

Assessing MACE over the entire follow-up period (active and passive) of the study postoperatively will be analyzed similarly (TABLE 21, FIGURE 2, TABLE 25) to the primary outcome with now the outcome being time (from index CABG surgery date) until the event of interest, MACE, or time-to-MACE during the entire follow-up (~ 6.5 years). Events from both the active and passive follow-up periods will be considered, whereas the primary analysis only included events from the active follow-up period. Only the first event among participants will be considered as the MACE event.

The hypotheses for the secondary aims of this study are:

H2: One-year composite MACE rate will be 6 percentage points lower in the open harvesting group and three-year composite MACE rates will be at least 8-10 percentage points lower in the open vein harvesting group compared to the endoscopic vein harvesting group.

H3: A significant smaller proportion of CABG subjects with SVGs harvested by open technique will experience MACE post-surgery compared to CABG subjects with SVGs harvested by endoscopic technique during the entire follow-up period.

The hypothesis H2 will be supported when the percent of participants experiencing MACE at one-year is 6% and at least 8% greater at three-years among those randomized to EVH vs. OVH, with a significant corresponding *p*-value < α observed for each test. The hypothesis H3 will be supported when an increased risk of MACE is observed among participants randomized to EVH, confirmed with a hazards ratio (HR) > 1.00 for EVH vs. OVH and a significant corresponding *p*-value. A total (recurrent) event analysis at various time points will also be explored comparing EVH and OVH.

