2.3.5 STS Score

The Society of Thoracic Surgeons (STS) score will be used to assess risk of operative mortality and morbidity of adult cardiac surgery on the basis of patient demographic and clinical characteristics. Higher scores are associated with greater risk.

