3.6 Sample Size

In the ROOBY study (CSP # 517) (Shroyer et al. 2009), 1-year MACE rates were 9.9% in the OVH group and 15.3% in the EVH group ($p=0.0025$). The executive committee for the REGROUP study assumed that during the REGROUP study, 15.5% of the participants in the EVH group will experience MACE in the first year post surgery. The committee also expects a 6 percentage point improvement in the 1-year MACE rate in the OVH group.

To detect the expected 6 percentage point difference in 1-year MACE rates between EVH (15.5%) and OVH (9.5%), a sample size of 545 in each group will be required at 85% power, 5% type-I error rate and with a two-sided test. Since, it would be possible to capture the majority of the MACE from the VA databases even if participants drop out before the one-year clinic visit, a relatively small inflation factor of 5% is used to inflate the sample size to account for the drop-outs. Thus, a total of 1,150 participants need to be randomized in the study to achieve the said power.

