6.3.4 Complexity of Coronary Artery Disease and Mortality and Morbidity Risks

The sample size, mean, median, SD, minimum, and maximum values for Syntax scores, indicating the complexity of coronary artery disease (CAD), will be presented, overall and by medical center, by MACE type, by age group, and by diabetes status as well as by treatment group (TABLES 14-17). Similar tables will be produced for the mortality and morbidity risk measures, VA Surgical Quality Improvement Program (VASQIP) and STS risk of mortality.

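### One-year and three-year MACE (secondary) are tested by an unadjusted chi-square although prognostic baseline data are already collected; pre-specified adjustment would add modest precision at almost no cost

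*SAP*

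**What the plan says.** - **Sizing.** SAP 3.6 derives the trial size from one-year MACE: "To detect the expected 6 percentage point difference in 1-year MACE rates between EVH (15.5%) and OVH (9.5"%). It then states: "a sample size of 545 in each group will be required at 85% power, 5% type-I error rate and with a two-sided test". A 5% allowance for drop-out brings the total to about 1,150.
- **Test.** SAP 7.2 says of the one-year comparison: "These two proportions will be compared using Pearson's chi-square test". Three-year MACE is handled in the same way. Protocol XVII.D.3 agrees. The Table 26 shell holds counts, percentages and a p-value, with no adjusted estimate.
- **Decision rule.** SAP 7.2 counts H2 as supported only if the one-year difference is 6 points and the three-year difference at least 8 points, each with a significant p-value.
- **Baseline data.** Form 02, completed for randomised subjects, holds date of birth, diabetes, and the SYNTAX, VASQIP and STS scores. SAP 2.3.3 to 2.3.5 state for each score that a higher value means greater risk. Of STS, SAP 2.3.5 says it "score will be used to assess risk of operative mortality and morbidity of adult cardiac surgery".
- **Use of the scores.** SAP 6.3.4 tabulates SYNTAX by centre, MACE, age group and diabetes, and adds: "Similar tables will be produced for the mortality and morbidity risk measures". No model in the SAP names any of the three scores.

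**The concern.** Randomisation makes the crude comparison unbiased, but part of the variation in one-year MACE is patient risk that was measurable before surgery. A pre-specified model that uses this information can target the same EVH-OVH risk difference with a smaller standard error, and it corrects for any chance imbalance in baseline risk. Elsewhere the SAP does adjust: a Cox model for time-to-MACE, logistic regression for leg wounds, ANCOVA for quality of life. The two fixed-time MACE proportions get nothing, although the one-year comparison is the one on which the 1,150 was calculated. At stake is the width of the interval and the power of a secondary comparison, not its validity.

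**Working it through.** **Inputs from the documents.** Rates 15.5% and 9.5%, 545 per arm, two-sided 5%, 85% power, 5% drop-out (SAP 3.6).

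**Assumed input.** The discrimination of the baseline variables for one-year MACE. The documents give none, so a range is shown.

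**1. The plan's own figure.** The pooled two-proportion formula without continuity correction gives 545 per arm at 85% power, an exact match. Power at 545 is 85.1%. Drop-out: 1090/0.95 = 1147.4, which agrees with the 1,147 in protocol Table 3 (Case 5), rounded to 1,150. The sizing is correct and assumes no gain from covariates.

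**2. Effect of adjustment on power.** If the covariates explain a share R² of the outcome variance, the variance falls by R² and the effective size is n/(1 − R²). R² was obtained from the c-statistic with a logistic model for one normally distributed risk score, calibrated to 9.5% and 15.5%. The last column is a simulation of 4,000 trials per row, chi-square against adjusted logistic test, with error of about 0.6 points.

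| Assumed c | R² | Effective n per arm | Power by formula | Simulated, crude → adjusted |
|---|---|---|---|---|
| 0.50 | 0 | 545 | 85.1% | – |
| 0.60 | 0.014 | 545/0.986 = 553 | 85.5% | 85.7% → 86.0% |
| 0.65 | 0.032 | 545/0.968 = 563 | 86.2% | 85.6% → 86.1% |
| 0.69 | 0.059 | 545/0.941 = 579 | 87.1% | 84.6% → 86.8% |
| 0.74 | 0.096 | 545/0.904 = 603 | 88.4% | 86.1% → 89.1% |

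A separate simulation of the risk difference gave variance reductions of about 1%, 3%, 7% and 10% at c = 0.60, 0.65, 0.70 and 0.75. The gain is therefore about 0.5 to 3.5 points of power.

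**3. Effect on the confidence interval.** The crude standard error at the planning rates is √(0.155·0.845/545 + 0.095·0.905/545) = 0.01995, so the 95% half-width is 1.96 × 0.01995 = 3.91 points. A variance reduction of 1% gives 3.91 × √0.99 = 3.89 points; 10% gives 3.91 × √0.90 = 3.71 points.

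**4. Effect on H2.** Read the one-year condition as an observed difference of at least 6 points. The standard error under the null is √(2p(1 − p)/545), with p the pooled rate.
- At the planning rates, p = 0.125: SE = 0.0200, z = 0.06/0.0200 = 2.99, p-value 0.003.
- At the worst case, p = 0.50: SE = 0.0303, z = 0.06/0.0303 = 1.98, p-value 0.048.

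With 545 per arm, an observed 6-point difference is always significant, so the p-value never decides the one-year condition. If the true difference is 6 points, the observed one reaches 6 in about half of trials. Simulation gave about 50% for both the crude and the standardised difference.

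**The case against.** The strongest case against runs as follows.

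- **Nothing is wrong with the test.** The chi-square is valid, matches the sample-size method and the protocol, and gives the promised power. This stands; the point is one of efficiency.
- **The endpoint is secondary.** A reader might infer, because the 1,150 is sized on one-year MACE, that the trial's main conclusion loses power. The documents do not support that. The primary analysis is time-to-MACE, with its own statement of 97.5% power at 532 per group (protocol XVII.B) and a covariate-adjusted Cox model (SAP 7.1).
- **The scores may not be wasted.** The Cox covariate list is open, so they could enter there. SAP 5.5.1 also allows imbalanced characteristics to become covariates in outcome analyses. Protocol IX.C gives subgroup evaluation as the reason for collecting the risk data. It would therefore be too strong to say that the scores can only ever be tabulated. These clauses still do not settle one-year MACE: the first concerns other analyses, and the second names no covariates and depends on what imbalance is seen.
- **The scores may be weak.** VASQIP and STS are described as 30-day or operative risk scores and SYNTAX as a measure of coronary complexity; none is presented as a predictor of one-year death, MI or revascularisation. This stands. At c = 0.60 to 0.65 the simulated gains are within simulation error.
- **H2 would not change.** A reader might take higher power to mean a better chance of supporting H2. Step 4 of the working shows that it does not.

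**Conclusion.** The point holds as a low-cost precision improvement for the secondary one-year and three-year MACE comparisons. Under assumed c-statistics of 0.60 to 0.75, one-year variance falls by about 1% to 10% and power for p<0.05 rises by about 0.5 to 3.5 points. The low end is plausible, because two of the three scores target operative mortality. Three-year MACE has no stated planning rates, so its gain was not sized. The benefit lies in the interval, the p-value and protection against chance imbalance in baseline risk. The documents do not support calling the chi-square an error or the trial underpowered, and the finding does not extend to the primary conclusion or to the probability of meeting H2. The H2 statement assumes that the 6-point condition means at least 6 points observed.

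**What to change.** In SAP 7.2:

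1. Pre-specify, for one-year and three-year MACE, a logistic model with arm and a fixed list of collected baseline covariates, for example STS risk on the logit scale, SYNTAX score, age and diabetes. One of STS and VASQIP is enough, since both are surgical mortality risk scores.
2. Report the standardised (marginal) EVH-OVH risk difference with 95% CI and p-value.
3. Give a simple rule for a missing score, such as mean imputation.
4. State whether the H2 difference condition is read on the crude or the standardised difference.
5. Keep the chi-square as supportive and add an adjusted row to Table 26.

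The cost is SAP wording and one model for each time point, with no new data. The covariate list must be fixed before outcome data by arm are seen.
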